For Aim 1, we additionally will bring together an Advisory Board of clinicians, administrators, suicide prevention experts, implementation scientists, and exposure theorists to refine the EBIS implementation strategy. [name] has close relationships with local community mental health clinics which will facilitate recruitment of Advisory Board members.

The Department of Psychiatry at the University of Pennsylvania's Perelman School of Medicine will provide the research infrastructure, physical accommodations, and resources necessary to ensure the project's success. The study team members have dedicated office space with password protected computer systems. Researchers will have the necessary word processing and statistical software for the project.

Acronym	Description
---------	-------------

SSAIs	suicide screening, assessment, and interventions
EBIS	exposure-based implementation strategy
CSSRS	Columbia Suicide Severity Rating Scale
SPI	Safety Planning Intervention
IAU	Implementation as Usual
EBPs	evidence-based practices
RA	research assistant
CSR	Chart Stimulated Recall
SPIRS	Safety Planning Intervention Rating Scale
ASI-3	Anxiety Sensitivity Index
PI	Principal Investigator
co-PI	Co-Principal Investigator
REDCap	Research Electronic Data Capture
CRCU	Clinical Research Computing Unit
CITI	Collaborative IRB Training Initiative
UPHS	University of Pennsylvania Health System
CPS	Center for the Prevention of Suicide
CMH	Center for Mental Health
PCs	Personal Computers
VAN	Value-Added Network
PHI	Protected Health Information
INSPIRE	Penn Interdisciplinary Network for Scientists Promoting Inclusion, Retention, and Equity
DSMB	Data and Safety Monitoring Board
GCP	Good Clinical Practice

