In sum, clinician anxiety and low self-efficacy are key implementation barriers to SSAI use but have not been implementation strategy targets. We will target these mechanisms by developing and pilot-testing an exposure-based implementation strategy (EBIS) for implementing the following evidence-based SSAs: the Columbia Suicide Severity Rating Scale (CSSRS) screener and assessment tool²² and the Safety Planning Intervention (SPI).²⁴ Data will inform an R01 to test EBIS at scale.

CHARACTERISTICS OF THE STUDY POPULATION:

1. Target Population and Accrual:

Aim 1: Aim 1 is a preparatory aim and does not involve human subjects research.

Aim 2: Aim 2 participants will be community clinicians (n = 20) recruited from any local community mental health clinics in the Philadelphia region.

Aim 3: Aim 3 participants are community clinicians (n = 40) recruited from 3-5 community mental health clinics in the City of Philadelphia.

2. Key Inclusion Criteria:

Aim 1: N/A

Aims 2 and 3: Participants must be:

- 1) Practicing mental health clinicians in the City of Philadelphia who provide direct mental health services to a treatment-seeking population.
**This may include mental health clinicians who are both licensed or unlicensed (i.e., intern or trainees seeking licensure or practicing under another provider's license). If the participant is a practicing clinician at a clinic from which we recruit, they will be eligible for the study. Potential licensures may include but are not limited to:
 - a. Licensed Family and Marriage Therapist (LMFT)
 - b. Licensed Clinical Social Worker (LCSW)
 - c. Licensed Social Worker (LSW)
 - d. Licensed Professional Counselor (LPC)
 - e. Licensed Mental Health Counselor (LMHC)
 - f. Licensed Clinical Professional Counselor (LCPC)
 - g. Licensed Professional Clinical Counselor of Mental Health (LPCC)
 - h. Licensed Clinical Mental Health Counselor (LCMHC)
 - i. Licensed Mental Health Practitioner (LMHP)
 - j. Clinical Psychologist (Licensed PsyD or PhD)
- 2) Proficient in the English language
- 3) Have access to a computer with internet connectivity

3. Key Exclusion Criteria:

Aim 1: N/A

Aims 2 and 3: Participants will be excluded if they do not see any mental health patients that are at risk for suicide (e.g., they screen out all high-risk patients for their individual practice). Participants will not be excluded based on sex, demographics, and or past experience.

4. Subject Recruitment and Screening:

Aim 1: N/A

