Aim 3: We will recruit clinicians for the pilot trial (n = 40) from 3-5 of our local partner community agencies with whom we have close relationships. Recruited agencies will be identified in collaboration with our Advisory Board and our partners within the City of Philadelphia Department of Behavioral Health. Clinics will be eligible if they have clinicians who provide direct mental health services to a mental health treatment-seeking population. We will only connect with clinicians working in these institutions if we receive clinic approval. We will not contact any clinicians if we do not have approval from clinic leadership or the clinician does not express interest in participating. To recruit clinicians, the study team will develop email scripts and flyers to disseminate to local agency partners who will in turn share these recruitment materials with their clinicians on staff. If it is preferred by the agency, the study team will collaborate with leadership in these agencies to identify a time for [name] or [name] or another senior member of the study team to attend a clinic team meeting (either virtually or in person) to present an overview of the study to interested clinicians. At this meeting, clinicians will complete a paper or electronic "consent to contact" via REDCap with their preferred contact information. Following the same procedures described in Aim 2 above, study staff will then follow up with interested clinicians to provide more information and to review all elements of informed consent.

Recruitment materials and scripts specific to the procedures in Aim 3 are included for the IRB's review.

5. Early Withdrawal of Subjects:

There is little risk associated with this study, and there is no safety concern associated with participation that would lead to participants being withdrawn from the study by the investigators. Importantly, exposure-based treatments upon which the EBIS implementation activities are based are generally well-tolerated with few, if any, side effects (see **Risks** below). As outlined in the informed consent document, there will be no consequences for any providers or other personnel who indicate interest and then do not enroll in the study. All participants will be free to withdraw their participation at any time by contacting study staff to inform them that they no longer wish to participate in the study.

6. Vulnerable Populations:

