We will use rapid cycle prototyping to iteratively refine EBIS based on feedback from up to 20 clinicians to optimize its acceptability and feasibility and identify early implementation challenges. Recruited clinician participants will receive approximately 3-4 hours of training in the CSSRS and SPI and the drafted EBIS prototype (exact sequencing of didactic and EBIS-based activities will be determined in Aim 1) either virtually or at a location on the University of Pennsylvania's campus. We will be in communication with clinic leadership during the study. As part of the communication, we will ask the leadership at each participating clinic if the study activities may be done on work time. Based on this response, we will communicate to all participants at each respective clinic site if the study activities are permitted to take place during work hours. To avoid selecting for a specific type of therapist, we will consider designing trainings to take place in smaller increments of time that are maximally feasible to be completed in the work setting (e.g., over the lunch hour); we will also clarify to leadership that study training activities with accompanying CEUs will satisfy licensure requirements for suicide training. Bachelor level RAs, shown to be effective in administering exposure, will be guided to administer EBIS by Co-PI [name], an exposure therapy expert. RAs will receive close supervision from [name].

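### The shared Aims 2 and 3 eligibility criteria do not bar clinicians who received the EBIS prototype in Aim 2 from being randomised in Aim 3

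*Combined protocol and SAP*

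**What the plan says.** Under Characteristics of the Study Population, items 2 and 3 (Key Inclusion Criteria, Key Exclusion Criteria), Aims 2 and 3 share one list. A clinician must practise in the City of Philadelphia, be proficient in English and have a computer with internet access. A note explaining that licensed and unlicensed clinicians both qualify contains the sentence "If the participant is a practicing clinician at a clinic from which we recruit, they will be eligible for the study". The single exclusion is "Participants will be excluded if they do not see any mental health patients that are at risk for suicide", followed by "Participants will not be excluded based on sex, demographics, and or past experience".

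Item 1 (Target Population and Accrual) describes the two pools: "Aim 2 participants will be community clinicians (n = 20) recruited from any local community mental health clinics in the Philadelphia region", and "Aim 3 participants are community clinicians (n = 40) recruited from 3-5 community mental health clinics in the City of Philadelphia". For the trial, item 4 (Subject Recruitment and Screening) names the source more closely: "We will recruit clinicians for the pilot trial (n = 40) from 3-5 of our local partner community agencies". The same sentence notes that the team has close ties with them. Both aims recruit through emails and flyers passed on by local agency partners, or through presentations at agency meetings.

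Study Procedures, Detailed Description, Aim 2 states what those clinicians are given: "Recruited clinician participants will receive approximately 3-4 hours of training in the CSSRS and SPI and the drafted EBIS prototype". In Aim 3, T1 is defined as baseline before training. IAU is the comparator, and EBIS is IAU plus the exposure-based component.

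**The concern.** Aim 2 delivers an early form of the experimental strategy, together with training in the same two practices that both Aim 3 arms teach. If an Aim 2 clinician enters Aim 3, two things go wrong. In IAU, that clinician is a control who has already had EBIS. In either arm, T1 is no longer measured before training, so part of any change has already happened.

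To the extent that the Aim 2 effect lasts, the EBIS-IAU contrast on anxiety, self-efficacy, adoption and fidelity is diluted. The primary acceptability and feasibility measures (AIM and FIM) may also be affected, because some raters will have met EBIS before and given the feedback that shaped it.

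**Working it through.** **1. Is there a bar anywhere?** The places that could hold one are the Aim 3 parts of Subject Recruitment and Screening, Method for Assigning Subjects to Groups, the Detailed Description of study procedures, and Consent Process. None excludes Aim 2 participants or requires that Aim 3 agencies differ from Aim 2 clinics.

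**2. Can the pools overlap?** Yes. The shared inclusion criterion requires practice in the City for both aims. Aim 2 may use any local clinic, and Aim 3 uses 3-5 local partner agencies. The document does not say how many clinicians are common to both.

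**3. Inputs.** Aim 3 randomises 40 clinicians 1:1, which agrees with the stated 20 and 20. Aim 2 has up to 20 clinicians. The plan disclaims power and gives no effect size, SD or alpha, so there is no sample-size figure to reproduce. Assumed here: k, the number of Aim 2 clinicians among the 40, and p, the share of the EBIS effect that they still carry.

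**4. Dilution.** Let D be the EBIS-IAU difference among clinicians new to EBIS. An Aim 2 clinician in IAU keeps pD and one in EBIS reaches D, so among Aim 2 clinicians the contrast is (1 − p)D. They make up k/40 of each arm in expectation, so

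expected contrast = D × [(1 − k/40) + (k/40)(1 − p)] = D × (1 − p·k/40).

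The largest loss under this model is at p = 1 (full persistence, no further gain), where the contrast shrinks by k/40. With p = 0.5, also an assumption, k = 8 gives 0.5 × 8/40 = 10%.

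**5. Chance that at least one lands in IAU.** With 20 of 40 places in IAU, this is 1 − C(40 − k, 20)/C(40, 20). For k = 4: 1 − (20·19·18·17)/(40·39·38·37) = 1 − 116,280/2,193,360 = 0.947.

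**6. Knock-on for a later trial.** Required sample size varies as 1/contrast². A trial sized on the diluted estimate would therefore need 1/(1 − k/40)² times the sample at p = 1.

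| Assumed k | Contrast kept, p = 1 | At least one in IAU | Sample-size multiplier, p = 1 |
|---|---|---|---|
| 0 | 100% | 0 | 1.00 |
| 2 | 95% | 76% | 1.11 |
| 4 | 90% | 95% | 1.23 |
| 8 | 80% | 99.8% | 1.56 |

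The last column applies only if the pilot's effect estimate is used to size the next trial. The plan says that its data will inform an R01 but does not say that they will be used in this way.

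**7. Does the analysis repair it?** Only in part. The Statistical Analysis section names organization as the one covariate. It also plans a baseline comparison of the arms, with adjustment for differences found. That can pick up a chance imbalance on a variable measured at T1. It cannot detect dilution shared equally by both arms, because no between-arm difference then appears. Prior Aim 2 participation is not listed in the described demographics survey. Per Table 2, role-play fidelity is first measured at T3 and AIM and FIM at T2, so these have no T1 value to compare.

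**The case against.** The strongest reply has four parts.

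First, the text can be read more narrowly. The sentence about practising clinicians belongs to a note on licensure and does not address re-enrolment. Past experience is listed beside sex and demographics, so it may mean professional background. The lists are headed as key criteria and need not be complete. Recruitment scripts and consent forms, which are not in the document, may restrict Aim 2 participants. This stands against any claim that a coordinator is obliged to admit them. It does not supply a bar, and the exclusion paragraph still gives a coordinator no written ground for refusal.

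Second, Aim 2 is a weaker exposure: about 3-4 hours with a draft, against 6 hours of training with a finalised manual plus 6 hours of consultation in Aim 3. This stands. It makes p = 1 an extreme case and k/40 an upper bound on the expected loss.

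Third, the affected arm contrasts are labelled exploratory, the pilot is expressly unpowered, and randomisation balances prior exposure in expectation. This lowers the stakes. But lack of power concerns precision, whereas controls with prior exposure change what is being compared, and balance between arms does not remove dilution.

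Fourth, the overlap may be zero. That is correct, and nothing in the document settles it.

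**Conclusion.** The gap in the criteria is real: as written, they do not keep Aim 2 clinicians out of Aim 3, and the planned analysis would not reveal shared dilution. The harm is possible but not shown. Its size rests on two unknowns, the overlap k and the persistence p. At full persistence with no further gain, the expected loss of contrast is 10% at k = 4 and 20% at k = 8; it is smaller at lower p and nil at k = 0. This is a worthwhile, inexpensive improvement, and the pilot's validity does not hinge on it.

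A reader might infer more, and the document does not support it:

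- **Permanent carry-over.** No duration is given for Aim 2 effects. The protocol calls training alone insufficient to change behaviour, and builds relapse prevention and follow-up consultation into EBIS to maintain gains. The point needs only that some effect persists to T1.
- **Half the contrast lost.** The arithmetic ceiling of 20/40 needs all 20 Aim 2 clinicians to work in the 3-5 Aim 3 agencies, enrol again and carry the full effect.
- **Advisory Board members as a second source.** The Aim 1 procedures class them as consulting members of the research team and not as participants.
- **Inflated acceptability ratings.** Having helped to refine EBIS could raise ratings, and repeating familiar content could lower them. The direction is unknown.

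**What to change.** Add an Aim 3 exclusion to Key Exclusion Criteria: clinicians who received any EBIS prototype session in Aim 2 are not eligible for Aim 3. State there that the past-experience sentence does not override it. Check each candidate against the Aim 2 enrolment list at eligibility screening.

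If any such clinician has already been randomised, flag them in the data. Report the AIM and FIM results and the arm contrasts with and without them.

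The cost is one sentence and a check against a list that the team already holds. The downside is the loss of a few willing clinicians from the Aim 3 recruitment pool. If there is no overlap, nothing is lost, and the protocol then documents that the IAU arm had no EBIS exposure from Aim 2.
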